3.10.2 Software

All statistical summaries and analyses of safety and efficacy data will be performed using SAS[®] 9.2 or higher (Statistical Analysis System, SAS-Institute, Cary, NC, USA) for Windows XP.

3.10.3 Disposition of Subjects

All subjects screened will be accounted for. A summary table will be presented specifying:

- The number of subjects screened
- The number of subjects randomized
- The number of subjects completing the active phase of the trial
- The number of subjects included in each analysis set
- The number of subjects withdrawn from the second vaccination (Group 1 only)
- The number of subjects prematurely discontinuing the trial (as well as the frequency of primary reasons for withdrawal/premature discontinuation)
- The number of subjects withdrawn from the third vaccination (Group 1 only)
- The number of subjects participating in remote (phone or email) FU Visit
- The number of subjects attending an on-site FU Visit

A listing will present all randomized subjects, time and date of completion or discontinuation with date of last dose of trial medication, date of discontinuation, reason for discontinuation and primary reason for withdrawal from second or third vaccination, if applicable.

All screening failures (subjects not eligible for the trial) will be listed including the reason why not eligible. Listings will also be presented for all violations in inclusion criteria and all exclusion criteria fulfilled.

All listings will be based on the screened subjects with screen failures and subjects randomized but not treated considered as two separate trial groups. However tables of the descriptive statistics for the demographics will only be produced for the FAS and PPS.

3.10.4 Demographic and Other Baseline Data

Descriptive statistics will be presented for the continuous demographic variables, age, age band, height, and body weight. Note that the date of the actual Screening Visit is used for age, age band, height and body weight calculations (hence also for BMI) and not the date of any Re-screening Visit.

Age is calculated using the following formula:

AGE = Year of Screening Visit – Year of Birth;
if Month of Screening Visit < Month of Birth then AGE → AGE – 1;
if Month of Screening Visit = Month of Birth
and Day of Screening Visit < Day of Birth then AGE → AGE – 1

Frequencies and percentages of subjects will be tabulated for the categorical variables sex, race and ethnicity in the same table by treatment group and overall. Percentages will be based on the total number of subjects in the relevant population.

Descriptive statistics for the demographic data will be produced by treatment group.

A Wilcoxon test for differences of the main baseline characteristics (age, body weight, height, BMI) will be performed between treatment groups.

A Fisher's exact test will be used to compare the gender, race and ethnicity between both treatment groups.

A summary of medical history by Preferred Term (PT) and System Organ Class (SOC) will be produced for each group.

Baseline signs and symptoms will be listed by body system and preferred term. Relative day of onset and duration of Baseline signs and symptoms will be calculated as described in [Section 3.8.3](#). Baseline signs and symptoms are defined as AEs with start date after the subject was screened for the trial but before the first vaccination was received. These events are to be reported.

3.10.5 Prior and Concomitant Medication

All prior medication will be summarized by Anatomical-Therapeutic-Chemical (ATC) class and Generic name according to the 2015/Q1 version of the World Health Organization Drug Dictionary (WHO-DD). All concomitant medication will be summarized by ATC class and Generic name for all subjects in the FAS.

The table/listing "Prior medication" includes the medication data where end date is before date of first administration of trial vaccine. The table/listing "Concomitant medication" includes ongoing medication or medication with missing end date or with end date after date of first administration of trial vaccine.

All listings will display the original dates as captured in the eCRF.

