17. Ten percent or greater risk of developing a myocardial infarction or coronary death within the next 10 years, e.g. using the National Heart, Lung and Blood Institute's Risk Assessment Tool: <http://cvdrisk.nhlbi.nih.gov/calculator.asp>  
NOTE: This criterion applies only to subjects 20 years of age and older
18. History of an immediate family member (father, mother, brother, or sister) who has had onset of ischemic heart disease before the age of 50 years
19. Clinically significant psychological disorder not adequately controlled by medical treatment
20. Active or history of chronic alcohol abuse and/or intravenous and/or nasal drug abuse (within the past 6 months)
21. History of anaphylaxis or any severe allergic reaction or serious adverse reaction to a vaccine
22. Eczema of any degree or history of eczema
23. People with active AD (characterized by pruritus, eczematous lesions, xerosis (dry skin), and lichenification (thickening of the skin and an increase in skin markings) or with a history of AD
24. People with chronic exfoliative skin disorders/conditions
25. People with active current Varicella zoster, Herpes zoster, impetigo, uncontrolled acne, Darier's disease, recent tattoos or skin piercing (until it is healed, but not within 4 weeks prior to trial vaccination), or any acute skin disorders of large magnitude, e.g., laceration requiring sutures
26. People with a tattoo that covers the vaccination injection area (preventing assessment of the area and interfering with a vaccination take assessment photograph)
27. Having received any vaccinations or planned vaccinations with a live vaccine (except trial vaccine) within 28 days prior to or after trial vaccination
28. Having received any vaccinations or planned vaccinations with a killed vaccine within 14 days prior to or after trial vaccination

29. Administration or planned administration of immunoglobulins and/or any blood products during a period starting from three months prior to administration of the vaccine and ending at trial conclusion
30. Use of any investigational or non-registered drug or vaccine other than the trial vaccines within 28 days preceding the first dose of the trial vaccine or planned administration of such a drug /vaccine during the trial period
31. Blood donation for the duration of the trial
32. Acute disease (illness with or without a fever)
33. Temperature  $\geq 100.4^{\circ}\text{F}$  ( $38.0^{\circ}\text{C}$ )

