3.7.2 Per Protocol Set

The Per Protocol Set (PPS) is the subset of subjects in the FAS who have received all vaccinations, completed all visits up until Visit 10 for Group 1 and Visit 4 for Group 2, and adhered to all protocol conditions. Subjects with only minor (not relevant) protocol deviations will be included into this dataset.

The decision whether a protocol deviation is major or minor will be made on a case-by-case basis in a data review meeting (DRM) prior to database lock.

Examples of major protocol violation are:

1. Premature discontinuation of the trial (the question “prematurely terminated the trial?” is answered with “yes” even where no other reason exists to exclude the subject from further participation in accordance with the protocol)
2. Subject did not meet all of the inclusion criteria
3. Subject met one or more of the exclusion criteria
4. Withdrawal from the second or third vaccination (Group 1)
5. Major vaccine preparation and administration deviation from specification as given in the protocol including cases where the subject fulfils at least one of the criteria specified in the protocol for withdrawal from vaccination
6. Major deviations of the visit window as determined during the DRM
7. Unallowed prior or concomitant medication
8. Missing lesion area data on Day 6-8 or Day 13-15 after ACAM2000[®] vaccination
9. Missing ELISA or PRNT titers at trial Day 0, Day 42 for subjects in Group 1 or Day 28 post ACAM2000[®] vaccination (Groups 1 and 2).

The primary endpoint dataset will be the PPS. All confirmatory testing is based on this subgroup. For further descriptive purposes, the same statistical procedures will be applied to the FAS.

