3.10 Analysis and Presentation Methods

3.10.1 Listings and Descriptive Statistics

All individual data entered in the eCRF and derived data will be listed as measured in the Individual Subject Data Listing.

For ELISA and PRNT titers descriptive statistics will be based on Geometric Means and confidence intervals (CI). For other, continuous parameters, measurements will be summarized by means of descriptive statistics (i.e. number of observations (N), mean, SD, minimum (Min), median, maximum (Max)) and categorical data will be summarized by means of frequency tables (i.e. count and percentages) and CI, if not stated otherwise.

All tables and listings will be sorted by scheduled visit (and subject, if appropriate).

All tables will be presented split by treatment groups (Groups 1 and 2). A comparison of the ACAM2000[®] vaccination phase will also be presented between Groups 1 and 2.

Repeat assessments/measurements and unscheduled assessments/measurements will be included in the Individual Subject Data Listing. All other repeat values will be listed in a separate listing.

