15.1.2.4 Demographic Data – ISS

15.1.2.5 Cardiac Risk Assessment – FAS

15.1.3 Medical History

15.1.3.1 Medical History by Preferred Term and System Organ Class – FAS

15.1.4 Prior and Concomitant Medication

15.1.4.1 Prior Medication, by ATC Class and Generic Name – FAS

15.1.4.2 Concomitant Medication, by ATC Class and Generic Name – FAS

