5.2 Listings

Section 16.2.1 Disposition and Demographics

- 16.2.1.1 Disposition
 - 16.2.1.1.1 Eligibility for Trial Participation – All Subjects
 - 16.2.1.1.2 Violation of Inclusion Criteria – All Subjects
 - 16.2.1.1.3 Exclusion Criteria Fulfilled – All Subjects
 - 16.2.1.1.4 Overall Assessment – All Subjects
 - 16.2.1.1.5 Withdrawal from Second or Third Vaccination – FAS (Group 1 only)
 - 16.2.1.1.6 Disposition – FAS

- 16.2.1.2 Demographic Data
 - 16.2.1.2.1 Demographic Data – All Subjects
 - 16.2.1.2.2 Cardiac Risk and Smallpox Vaccination History – All Subjects

- 16.2.1.3 Medical History
 - 16.2.1.3.1 Medical History – FAS
 - 16.2.1.3.2 Baseline Signs and Symptoms – FAS
 - 16.2.1.3.3 Abnormal Physical Examination at Screening – FAS

- 16.2.1.4 Prior and Concomitant Medication
 - 16.2.1.4.1 Prior Medication – FAS
 - 16.2.1.4.2 Concomitant Medication – FAS

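### SAP 3.10.5 leaves a medication that ended on the day of first vaccination in neither the prior nor the concomitant medication output

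*SAP*

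**What the plan says.** SAP 3.10.5 defines the two medication outputs by end date. The prior medication output "includes the medication data where end date is before date of first administration of trial vaccine". The concomitant medication output "includes ongoing medication or medication with missing end date or with end date after date of first administration of trial vaccine". The section applies each rule to the table and to the listing alike.

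The SAP's list of outputs (sections 5.1 and 5.2) names two medication tables, 15.1.4.1 (prior) and "15.1.4.2 Concomitant Medication, by ATC Class and Generic Name – FAS", and two medication listings, 16.2.1.4.1 (prior) and "16.2.1.4.2 Concomitant Medication – FAS". No other medication output is named.

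Other text bears on the point:

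- SAP 3.8.1 gives imputation rules for partial medication dates, but no rule for an end date equal to the first vaccination date.
- SAP 3.8.2 does settle the same-day question for adverse events: if the start time is missing and the start date is a vaccination date, the event goes to that vaccination's period.
- SAP 3.8.1 and 3.10.1 and Protocol 9.6 say in general terms that all eCRF or CRF data will be listed.

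**The concern.** Two rules that together should cover every medication record leave out one date. That date is one on which records can be expected. Subjects are observed for at least 30 minutes after vaccination with medical treatment at hand (Protocol 4.2.2), and Protocol 8.2.2 requires the start and end of each concomitant treatment to be recorded. A drug given once for a reaction on Day 0 has its start and end on Day 0.

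What is at stake is whether the concomitant medication table and listing are complete. A program that follows the SAP drops these records from both. A program that keeps them departs from the SAP without a documented reason. The day affected is also not the same kind of day in the two groups: it is an MVA-BN day in Group 1 and the ACAM2000 day in Group 2.

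**Working it through.** No figure in the plan can be reproduced here, since the point is one of logic. Let V1 be the date of first vaccination. The inputs are the two rules in SAP 3.10.5:

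- Prior: end < V1.
- Concomitant: ongoing, or end date missing, or end > V1.

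The comparisons use dates only. That fits the SAP's definition of trial day, which disregards the time of vaccination.

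Applying both rules to each possible state of the end date, as written and with the concomitant limb changed to end ≥ V1:

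| End date | Prior | Concomitant, as written | Concomitant, with ≥ |
|---|---|---|---|
| V1 − 1 day | yes | no | no |
| V1 | no | **no** | yes |
| V1 + 1 day | no | yes | yes |
| Missing | no | yes | yes |
| Ongoing | no | yes | yes |

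As written, one state is unassigned: an end date equal to V1. With ≥, each state falls in exactly one category, with no gap and no overlap.

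Next, which vaccination days are affected. V1 is Day 0 in both groups.

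- Group 1 is vaccinated on Days 0 (MVA-BN), 28 (MVA-BN) and 56 (ACAM2000). A medication ending on Day 28 or Day 56 satisfies end > V1, because 28 > 0 and 56 > 0, and is counted. Only one ending on Day 0 is dropped.
- Group 2 is vaccinated on Day 0 (ACAM2000) only. A medication ending that day is dropped.

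So the gap falls on one of three vaccination days in Group 1 and on the only one in Group 2.

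On scale, the documents give no rate. If one assumes, purely for illustration, that 2% to 10% of subjects have a medication ending on Day 0, then with 220 subjects per group:

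- 0.02 × 220 = 4.4
- 0.10 × 220 = 22

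That is about 4 to 22 subjects per group with at least one unassigned record. Same-day drugs left as ongoing, or without an end date, are captured under the present wording and do not count towards this.

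**The case against.** The strongest reply is that little is lost. Four parts of it deserve an answer.

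**The data are listed anyway.** SAP 3.8.1 and 3.10.1 and Protocol 9.6 promise a listing of everything in the eCRF or CRF. This stands in part. It would be wrong to infer that the record disappears from all listings. But no named medication listing carries it, SAP 3.10.5 applies its rules to the listings explicitly, and the general statement does not put the record back into the summary table.

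**The Per Protocol Set is not affected.** SAP 3.7.2 gives "Unallowed prior or concomitant medication" as an example of a major violation, so a reader might infer that a prohibited medication on Day 0 would go unseen and its taker stay in the set used for both co-primary analyses. The documents do not support that. Violations are judged case by case in a data review meeting, and nothing says that the meeting works from the 3.10.5 listings. There are other routes: deviations are recorded on the CRF (Protocol 13.3), eligibility is re-checked at Visit 1, and exclusion criteria fulfilled have their own listing (16.2.1.1.3). A non-trial killed vaccine given on Day 0 falls under the criterion "Having received any vaccinations or planned vaccinations with a killed vaccine within 14 days prior to or after trial vaccination", a live one under exclusion 27, and meeting an exclusion criterion is itself an example of a major violation. A single-day corticosteroid is not clearly prohibited: exclusion 6 and the withdrawal criterion in Protocol 4.2.5 concern chronic use of more than 14 days. This part of the reply stands.

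**No planned ACAM2000-phase comparison is distorted.** SAP 3.10.1 says that a comparison of the ACAM2000 "vaccination phase will also be presented between Groups 1 and 2". A reader might infer that same-day treatment would be missing from Group 2 only in such a table. On the ACAM2000 day taken alone that would be so, but no medication output specific to that phase is named. In the planned overall tables Day 0 is missing in both groups. This part also stands.

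**The safety endpoints are intact.** Immediate reactions are recorded as adverse events, and SAP 3.8.2 settles same-day adverse events. This stands too. The treatment given for the reaction is what the medication outputs omit.

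**Conclusion.** The gap is real and follows from the wording alone. A medication whose recorded end date equals the date of first vaccination is in neither planned medication table and neither named medication listing. Because same-day ties are settled for adverse events but not for medications, it looks like an oversight.

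Its consequence is an incomplete descriptive account of concomitant medication. No co-primary test, sample size or power figure depends on it, and an effect on membership of the Per Protocol Set is not shown. How many records are affected is unknown; the range of about 4 to 22 subjects per group rests entirely on the assumed 2% to 10%.

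The conclusion assumes that SAP 3.10.5 is programmed as written. It is a minor correction, but worth making because the rule as stated produces a wrong table and the remedy is almost free.

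**What to change.** In the concomitant rule of SAP 3.10.5, replace *after* with *on or after* in the end-date condition. Leave *before* in the prior rule unchanged. Every record then falls in exactly one of the two outputs, and the named listings agree with the general statement in SAP 3.10.1 that all eCRF data are listed.

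The change is a few words in the SAP and one comparison operator in the program, with no new data. The SAP foresees a final version before database lock, which is the natural place for it. The small downside is that a medication stopped earlier on Day 0, before the vaccination, is shown as concomitant.

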3.10.6 Compliance

Compliance will be evaluated with respect to the number of vaccine doses received and the number of memory aids completed.

3.10.7 Immunogenicity Analysis

The co-primary immunogenicity objective of the trial is to assess non-inferiority of MVA-BN[®] compared to ACAM2000[®] in terms of PRNT antibody response at the Peak Visits (Day 42 for Group 1 and Day 28 for Group 2).

Suppose m_1 is the PRNT \log_{10} titer mean in Group 1 and m_2 is the PRNT \log_{10} titer mean in Group 2. The test of non-inferiority will be applied for the following hypothesis:

$$H_0: m_1 - m_2 \leq -\Delta \text{ versus } H_1: m_1 - m_2 > -\Delta \text{ where}$$

Δ is the non-inferiority margin. For the PRNT the non-inferiority margin will be 0.301 on the \log_{10} scale which is equivalent to a doubling on the original titer scale for the GMT. This is the same Δ for the PRNT as was used for the assessment of non-inferiority of ACAM2000[®] to Dryvax[®] (ACAM2000 VRBPAC Briefing Document, April 2007).

The above hypotheses will be tested for the PRNT using a t-test on the difference of the two means based on the assumption that the \log_{10} titers are normally distributed (which has been the case in all previous MVA-BN[®] studies). Specifically, a one-sided 97.5% confidence interval for the difference of the \log_{10} titer means (based on the assumption of a common standard deviation [SD]) will be calculated. If the lower limit of this confidence interval is greater than $-\Delta$, then the null hypothesis will be rejected and non-inferiority of MVA-BN[®] to ACAM2000[®] will have been demonstrated.

For better interpretation the primary analysis will be presented in terms of the ratio of the GMTs, which is equivalent to taking the antilog of the differences in the \log_{10} means. Similarly the corresponding confidence intervals are presented on the original titer scale by taking the antilog of the CIs calculated on the \log_{10} scales. In this way, non-inferiority of MVA-BN[®] to ACAM2000[®] will be demonstrated if the lower limit of CI of the ratio of the GMTs lies within the interval above $\frac{1}{2}$. This interval is obtained as the antilog of the $-\Delta$.

A similar analysis will be conducted for descriptive purposes on the ELISA \log_{10} titer means. This will be done as secondary endpoint. The non-inferiority margin is chosen to be 0.176 for the ELISA on the \log_{10} scale (which is equivalent to a factor of $\frac{2}{3}$ on the original titer scale for the GMT).

All immunogenicity results will be listed. Tables and figures will be prepared for the PPS, ISS and the FAS. All of the following analyzes will be performed for results generated using both the PRNT and ELISA.

Seropositivity rates

Vaccinia-specific seropositivity rates will be presented by group for all sampling visits along with the Clopper-Pearson 95% confidence intervals (CIs) of the seropositivity rates. In addition, the Fisher's exact test will be performed between groups to determine if there is any difference in seropositivity rates.

Seroconversion rates

Vaccinia-specific seroconversion rates will be presented by group for all post baseline sampling visits along with the Clopper-Pearson 95% CIs of the seroconversion rates. In addition, the

Fisher's exact test will be performed between groups to determine if there is any difference in seroconversion rates.

Seroconversion rates will be presented graphically in a bar chart by visits differentiated by groups.

Geometric Mean Titer

GMTs will be calculated at all sampling visits for each group. GMTs and upper and lower confidence limits will be displayed to one decimal place.

Descriptive statistics will be derived by visit including number of observations available at each visit (n), GMT, with 95% CI (derived by the antilogarithm of the 95% CI of the \log_{10} titer transformations).

The ratio of the GMTs will be presented between groups (Group 1 / Group 2) for Peak Visits along with the 95% CI. This ratio will be used to perform the non-inferiority analysis for the Peak Visit GMTs.

GMTs will be presented graphically in a line chart by visits differentiated by groups. The GMT will be displayed on the Y axis using a base 10 exponential axis, while visits will be displayed on the X axis by week.

Correlation of ELISA and PRNT results

Pearson's correlation coefficient (with associated CI) for \log_{10} titers measured by ELISA and PRNT at each post baseline sampling visit will be calculated per group with the associated p-values and 95% CIs for the PPS, ISS and FAS. The correlation will also be presented on a scatter plot by group.

3.10.8 Efficacy Analysis

The co-primary efficacy endpoint of the trial is the MLA in mm^2 after scarification with ACAM2000. The primary analysis assesses if the AAR (based on the MLA) is significantly above $\lambda=40\%$ using the HL method for calculating the non-parametric confidence interval as described in [Section 3.3](#) and implemented using the HL option in the SAS procedure NPAR1WAY.

In addition, the median for each group (and overall for both groups) will be calculated along with the 95% non-parametric confidence intervals for the median ([Hahn, 1991](#)). This will be obtained using the SAS Univariate procedure with the option CIPCTLDF. In addition, the minimum and maximum values will be displayed.

A similar secondary supportive analysis will be performed using the PB method (described in [Appendix 6.1](#)). A similar secondary descriptive analysis will also be performed to calculate the confidence interval of the AAR (based on the MLD) using the HL method for:

- lesion area (mm²) at Day 6-8
- lesion area (mm²) at Day 13-15

and the DAR using the investigator measurements of:

- maximum lesion diameter (mm)
- lesion diameter (mm) at Day 6-8
- lesion diameter (mm) at Day 13-15

